3.1 Enrollment status

The following summaries will be provided in each cohort separately for the FAS overall, and for both treatment groups:

1. Number (%) of patients who were randomized
2. Number (%) of patients who received at least one dose of study treatment after randomization

Number (%) of patients screened will be summarized by country and center. In addition, the number (%) of patients randomized will be summarized by country, center and treatment group.

For patients who are screen failures, the reasons for not completing screening will be summarized based on “Screening Phase Disposition” eCRF.

3.2 Background and demographic characteristics

The FAS will be used for all baseline disease characteristics and demographic summaries and data listings. Summaries will be presented in each cohort separately for the FAS overall and for both treatment groups to assess baseline comparability. No inferential statistics will be provided.

3.2.1 Basic demographic and background data

Descriptive statistics (mean, median, standard deviation, minimum, maximum) will be presented for continuous variables. The number and percentage of patients in each category will be presented for categorical variables. This analysis will include the following: Age, gender, race, ethnicity, body mass index (BMI) and ECOG performance status at baseline.

BMI at Baseline will be calculated using the following formula, i.e., $BMI \text{ (kg/m}^2\text{)} = \text{weight (kg)} / (\text{height (cm})/100\text{)}^{**2}$ using weight at Baseline.

A breakdown of the age distribution according to EUDRACT required categories will be provided: Adolescents (12-17 years), Adults (18-64 years), Elderly (≥ 65 years).

3.2.2 Diagnosis and extent of cancer

This analysis will include the following: primary site of cancer, predominant histology/cytology, histological grade, stage at initial diagnosis, stage at time of study entry, time since initial diagnosis of primary site, time from initial diagnosis to first recurrence/progression, time since most recent relapse/progression (where last treatment was in the (neo-)adjuvant or advanced disease settings), presence/absence of target and non-target lesions, number of metastatic sites, metastatic sites, HER2 receptor status, estrogen receptor (ER) status, progesterone receptor (PgR) status and hormone receptor (ER and/or PgR) status.

Note: The variables ‘presence/absence of target and non-target lesions’ will be based on the data collected on target/non-target lesion assessment according to RECIST 1.1 (Appendix 3 of the protocol) and documented in the eCRF.

3.2.3 Medical history

Medical history and ongoing conditions, including cancer-related conditions, will be summarized and listed. Separate summaries will be presented for ongoing and historical medical conditions. The summaries will be presented by system organ class and preferred term. Medical history/current medical conditions are coded using the latest version of Medical Dictionary for Regulatory Activities (MedDRA) terminology available at the time of the analyses. The MedDRA version used for reporting will be specified in the CSR and as a footnote in the applicable tables/listings.

3.2.4 Prior anti-neoplastic therapy

The number (%) of patients receiving prior anti-neoplastic medication, prior anti-neoplastic radiotherapy and prior anti-neoplastic surgery respectively will be summarized.

Prior anti-neoplastic therapy will be summarized for each treatment group by therapy type (surgery, radiotherapy, chemotherapy, hormonal therapy etc.), disease setting, last therapy before study entry and its outcome (type of therapy, setting, and best response). Number of lines of prior medication therapy, prior chemotherapy, and prior hormonal therapy will be summarized by treatment group in any setting and in the metastatic setting. In addition, number of lines of prior chemotherapy in the neo-/adjuvant setting will also be summarized by treatment group.

In addition, number (%) of patients who received any hormonal therapy (irrespective of given in combination with chemotherapy or biologic or targeted therapy), any aromatase inhibitors, any hormonal therapy other than aromatase inhibitors in any setting and in the metastatic setting, any prior CDK4/6 inhibitors will be summarized by treatment group.

Patients exhibiting primary & secondary endocrine resistance will be summarized based on the ESMO (ref) definition, vs patients exhibiting endocrine sensitivity:

- **Primary resistance** = Relapse < 24 months while on ET in adjuvant setting or progression < 6 months while on ET in metastatic setting
- **Secondary resistance** = Relapse ≥ 24 months while on ET in adjuvant setting or relapse < 12 months after end of ET in adjuvant setting or progression ≥ 6 months while on ET in metastatic setting
- **Endocrine sensitive** = Relapse ≥ 12 months after end of ET in adjuvant setting or progression ≥ 12 months after end of ET in metastatic setting

The patient population will be summarized additionally by presenting the number (%) of patients with:

- relapsed with documented evidence of progression more than 12 months from completion of (neo)adjuvant endocrine therapy with no treatment for metastatic disease
- relapsed with documented evidence of progression more than 12 months from completion of (neo)adjuvant endocrine therapy and then subsequently progressed with

documented evidence of progression while on or after only one line of endocrine therapy for metastatic disease

- relapsed with documented evidence of progression while on (neo) adjuvant endocrine therapy or within 12 months from completion of (neo)adjuvant endocrine therapy with no treatment for metastatic disease
- newly diagnosed advanced breast cancer, then relapsed with documented evidence of progression while on or after only one line of endocrine therapy

The medication therapy type of any combination therapy will be classified based on the following order: chemotherapy, biologic therapy, targeted therapy, hormonal therapy. For example, a combination therapy of chemotherapy and hormonal therapy will be classified as chemotherapy.

Last hormonal therapy prior to study entry will be summarized by type of aromatase inhibitors, anti-estrogen therapy, disease setting, duration of hormonal therapy in adjuvant setting and best overall response at last hormonal therapy in the metastatic setting.

Last hormonal therapy refers to hormonal medication received in the last regimen. If multiple hormonal therapy medications are given as part of last regimen, then last hormonal therapy medications are selected based on the latest start date among the hormonal therapy medications. Standard imputation rules will be applied for dates of prior anti-neoplastic therapy (medication, radiotherapy and surgery).

Separate listings will be produced for prior anti-neoplastic medications, radiotherapy, and surgery.

3.3 Protocol deviation summaries

The number and percentage of patients in the FAS with any protocol deviation will be summarized by deviation category (as specified in the Study Specification Document).

Protocol deviations leading to the exclusion from the Per Protocol Set will also be summarized.

All protocol deviations will be listed. Summaries will be presented in each cohort separately for the FAS overall and for both treatment groups.

Additional protocol deviation summaries will be provided to address the potential impact of COVID-19 pandemic in each cohort. The number and percentage of patients in the FAS with any protocol deviation with one of the following relationships will be summarized by deviation category: COVID-19 health status related, COVID-19 situation: Site issue, COVID-19 situation: Lockdown / Quarantine of patient, COVID-19 situation: Patient concern, COVID-19 situation: Drug supply issue and COVID-19 situation: Other.

3.4 Groupings for analysis

The number and percentage of patients in each analysis set (definitions are provided in [Section 2.3](#)) will be summarized in each cohort separately, by treatment arm and randomization stratum (presence of lung and/or liver metastases, previous treatment with any CDK4/6 inhibitor based on data obtained from the IRT system).

Discrepancies between stratum recorded in IRT at the time of randomization and actual stratum recorded in the clinical database will be summarized.

3.5 Patient disposition

The FAS will be used for the patient disposition summaries, which will be summarized in each cohort separately overall, and for both treatment groups.

Based on the ‘End of Treatment Disposition’ and ‘End Post Trt Phase Disposition’ CRF there will be one combined by-treatment summary showing:

1. Number (%) of patients who are still on-treatment (based on the absence of the ‘End of Treatment Disposition’ eCRF)
2. Number (%) of patients who discontinued study treatment (based on the ‘End of Treatment Disposition’ eCRF)
3. Reasons for study treatment discontinuation (based on ‘End of Treatment Disposition’ eCRF)
4. Number (%) of patients who entered the post-treatment evaluations (based on ‘End of Treatment Disposition’ eCRF)
5. Number (%) of patients who discontinued from the post-treatment evaluations (based on the ‘End Post Trt Phase Disposition’ eCRF)
6. Reasons for discontinuation from the post-treatment evaluations phase (based on ‘End of post treatment follow up disposition’ eCRF).

3.6 Study treatment

Duration of study treatment exposure, cumulative dose, dose intensity (DI) and relative dose intensity (RDI) will be summarized by treatment. The number of patients with dose reductions/interruptions, and the reasons, will be summarized and listed. Details of the derivations and summaries are provided in the following sections.

Summaries will be presented for the Safety set by treatment arm, in each cohort separately as well as both cohorts combined.

Data handling

The following rule should be used for the imputation of date of last administration (please refer to [Section 2.1.3](#)) for a given study treatment component:

Scenario 1: If the date of last administration is completely missing and there is no EOT eCRF, the subject is considered as on-going:

The subject should be treated as on-going and the cut-off date should be used as the last dosing date.

Scenario 2: If the date of last administration is completely or partially missing and the EOT eCRF is available (prior to any death date or withdrawal of consent date, if available):

Case 1: The date of last administration is completely missing, and the EOT visit date is complete, then this latter date should be used.

Case 2: Only Year(yyyy) of the dose end date is available and yyyy < the year of EOT date:

Use Dec31yyyy

Case 3: Only Year(yyyy) of the dose end date is available and yyyy = the year of EOT date:

Use EOT date

Case 4: Both Year(yyyy) and Month (mm) are available for the date of last administration, and yyyy = the year of EOT date and mm < the month of EOT visit:

Use last day of the Month (mm).

After imputation, compare the imputed date with the start date of that specific record, if the imputed date is < start date of that record

Use the start date of that record.

Subjects with missing start dates are to be considered missing for all study treatment component related calculations described in [Section 3.6](#) and no imputation will be made. If the date of first administration is missing, then the date of last administration should not be imputed.

3.6.1 Duration of study treatment exposure

Duration of exposure to study drug (for alpelisib/placebo and fulvestrant) is defined according to dosing regimen for each study drug as outlined in [Section 2.1.6](#).

Duration of exposure (days) = (last date of exposure to study drug) – (date of first administration of study drug) + 1

Duration of exposure to study treatment is considered by taking into account the duration of exposure to each study drug:

Duration of exposure (days) = (last date of exposure to study treatment) – (date of first administration of study treatment) + 1,

The duration includes the periods of temporary interruption. ‘Date of first administration of study drug/treatment’ and ‘last date of exposure to study drug/treatment’ are defined in Sections [2.1.2/2.1.4](#) and [2.1.6 respectively](#).

Duration of exposure to study drug/treatment will be categorized into time intervals (<1 month, at least 1 month, at least 2 months etc.). In addition, summary statistics will be displayed.

Note: If the last record in DAR CRF is a zero dose, this record will not be used in the analyses.

To assess the impact of specific adverse events of special interest on exposure to study treatment the following summaries are added:

- Duration of exposure to study drug for patients who developed hyperglycemia during the study

- Duration of exposure to study drug for patients who developed hyperglycemia during the study and started anti-diabetic medication
- Duration of exposure to study drug for patients who developed hyperglycemia during the study and started anti-diabetic medication by hyperglycemia diagnosis status
- Duration of exposure to study drug for patients who developed rash during the study
- Duration of exposure to study drug for patients who developed rash during the study and started anti-rash medication

Patients who developed hyperglycemia [rash] during the study are defined as those patients with any on-treatment CTC Grade 1 or higher AESI. Hyperglycemia diagnosis status is defined in Section [3.13.1](#). Anti-diabetic medications are defined by medications where ATC code=A10 [Drugs used in diabetes]. Anti-rash medications are defined by medications where ATC codes in the following categories:

- R06A [Antihistamines for systemic use]
- D07 [Topical dermatological corticosteroids]
- H02 [Corticosteroids systemic]

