6.3.2.1.2 Guidelines for the treatment of study drug induced skin toxicity

Skin toxicity is a class-effect adverse event observed with PI3Ki/mTORi agents.

Close monitoring of potential skin reactions will be performed at each planned visit and will be reported as adverse event. The most frequent skin adverse events reported are: maculopapular rash (only a minority present acneiform rash); pruritus and dry skin. The onset is typically within the first 2 months of treatment start and is reversible with adequate comedication and treatment interruption if needed. Skin reactions may improve over several weeks. Consultation with a dermatologist is highly recommended for better assessment and management of alpelisib-induced skin toxicity at any grade, and mandated if severe cutaneous reaction like

Stevens-Johnson-Syndrome, Toxic Epidermal Necrolysis or Erythema multiforme or Drug Reaction with Eosinophilia and Systemic Symptoms (DRESS) is suspected. Workup for skin toxicity events includes skin photography, a complete blood count with differential, and a full chemistry panel. A paired skin biopsy should be obtained (from both affected and an unaffected skin area) for local histopathology assessment to further assess the skin toxicity, especially to confirm suspected diagnosis of any severe cutaneous reactions.

Skin photographs must be taken and skin biopsy must be performed in case of Grade 4 skin toxicity and any grade of suspected severe cutaneous reactions. In case of Grade 3 skin toxicity, Novartis recommends that photographs are taken and a skin biopsy is performed.

Skin biopsy will be sent to a Novartis designated laboratory, together with dermatologist and pathologist reports, if available, for further research purpose on the pathology and mechanism of PI3K inhibitor treatment induced skin toxicity

Antihistamines administered prior to rash onset may decrease incidence and severity of rash based on Study CBYL719C2301; therefore, at the Investigator's discretion, non-sedating antihistamines (e.g. cetirizine (Zyrtec[®]), fexofenadine (Allegra), loratadine (Claritin)) may be used as prophylactic treatment to reduce severity of rash in all patients and especially for patients with a history of atopy such as allergic rhinitis, asthma, atopic dermatitis, or drug allergies.

For any grade of severe cutaneous reactions, alpelisib treatment must be permanently discontinued without any re-challenge.

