6.3.2.1.3 Guidelines for the treatment of alpelisib induced hyperglycemia

Alpelisib, like other PI3K inhibitors, may affect glucose homeostasis which could result in increases of plasma glucose and insulin resistance (Busaidy 2012). Alpelisib induced hyperglycemia is generally manageable with adequate antidiabetic treatment. Alpelisib induced hyperglycemia typically occurs within the first month of treatment. Patients with pre-diabetes (i.e. FPG 100 – 125 mg/dl; 5.6 - 6.9 mmol/L) and those with an established diagnosis of type 2 diabetes mellitus should be monitored carefully, thus allowing an early detection and prompt management of increases in FPG while on alpelisib/placebo treatment. However all patients, even those with FPG within normal limits at screening, may develop alpelisib induced hyperglycemia. Patients should always be instructed to follow dietary guidelines provided by the American Diabetes Association, e.g. small frequent meals, low carbohydrate content, high fiber, balancing carbohydrates over the course of the day; three small meals and 2 small snacks rather than one large meal and exercise, as appropriate.

Detailed guidelines for management of alpelisib induced hyperglycemia is provided in [Table 6-3](#) following discussion with an advisory board. This includes early administration of metformin. Metformin may be titrated to a daily dose of 1000 mg BID. Local protocols per standard clinical practice may be followed for monitoring and managing hyperglycemia. Fasting plasma glucose may be performed both locally and/or centrally for rapid availability for safety evaluation and management guidance. Special attention should be paid to the risk of hypoglycemia in patients interrupting alpelisib treatment and concomitantly receiving insulin and/or sulfonylureas. Due to the short half-life of alpelisib, all glucose lowering medications should be discontinued when alpelisib is stopped.

Consultation with a diabetologist is highly recommended for better assessment and management of alpelisib-induced hyperglycemia.

6.3.2.1.4 .Follow-up on amylase or lipase elevation (\geq CTCAE Grade 3)

Patient with amylase or lipase elevation \geq CTCAE Grade 3 must be tested weekly (or more frequently if clinically indicated) until \leq Grade 1 (or baseline). After resumption of dosing, continue to test weekly for one additional cycle. If no reoccurrence of \geq Grade 2 event, continue monitoring every cycle.

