2.1.9 On-treatment assessment/event

Safety summary tables and selected summaries of deaths will summarize only on-treatment assessments/events.

An on-treatment adverse event is defined as any adverse event reported in the following time interval (including the lower and upper limits):

- date of first administration of study treatment; date of last administration of study treatment + 30 days

In addition, an AE that started in the screening phase and was ongoing in the treatment phase will not be summarized unless it has worsened in severity.

An on-treatment assessment is defined as any assessment performed after the date of first administration of study treatment i.e. assessments performed in the following time interval (including the lower and upper limits):

- date of first administration of study treatment + 1; date of last administration of study treatment + 30 days

If the last date of study treatment is missing, on-treatment assessments/events include any assessment/event recorded in the database and which occur after the start date of study treatment.

Data listings will include all assessments/events, flagging those which are not on-treatment assessments/events.

Note: The date of first administration of study treatment and the date of last administration of study treatment are defined in sections [2.1.4](#) and [2.1.5](#), respectively.

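### The five exposure summaries for hyperglycemia and rash in SAP 3.6.1 cannot assess the events' impact on exposure, because patients are grouped by a post-baseline event, the clock starts at first dose and there is no comparator

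*SAP*

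**What the plan says.** SAP 3.6.1 adds five summaries under the sentence "To assess the impact of specific adverse events of special interest on exposure to study treatment the following summaries are added". The first is "Duration of exposure to study drug for patients who developed hyperglycemia during the study". The second narrows this to "Duration of exposure to study drug for patients who developed hyperglycemia during the study and started anti-diabetic medication", and the third splits that subset by baseline hyperglycemia diagnosis status. The last two are the rash counterparts of the first and second.

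The only exposure measure defined for a study drug is "Duration of exposure (days) = (last date of exposure to study drug) – (date of first administration of study drug) + 1". Patients who developed the event "are defined as those patients with any on-treatment CTC Grade 1 or higher AESI". Under SAP 2.1.9 an adverse event is on-treatment if it falls in the interval "date of first administration of study treatment; date of last administration of study treatment + 30 days", and SAP 2.1.5 takes the last administration of any component of study treatment.

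Section 3.6.1 gives no landmark, no clock starting at onset, no time-dependent grouping and no comparison group. SAP 3.6 says only that treatment summaries are shown by arm, in each cohort and combined.

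On timing, Protocol 6.3.2.1.3 states "Alpelisib induced hyperglycemia typically occurs within the first month of treatment", and Protocol 6.3.2.1.2 says of skin reactions "The onset is typically within the first 2 months of treatment start".

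**The concern.** Group membership is settled after baseline, but exposure is counted from before it was settled. The time between first dose and onset is credited to the event group although nobody could yet have been classified. Patients who stay on treatment longer also have more opportunity to have the event recorded and, in three of the tables, to start a medication for it. Both features push exposure in event patients upward for reasons unrelated to the event.

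The question behind the tables is a real one, since Protocol Table 6-3 calls for interrupting, reducing or permanently stopping alpelisib/placebo for some grades of both events. A reader who takes the lead-in at its word would set these medians beside the all-patient exposure in the same section. A similar or longer figure could then be read as evidence that the events do not shorten treatment.

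**Working it through.** The plan states no figure for these tables, so there is nothing to reproduce. The check asks what they would show if the event had no effect on exposure.

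**Inputs.**
- Exposure: exponential, with the design median PFS as proxy (an assumption). Protocol 10.8 gives 7.0 months on control and a hazard ratio of 0.6, so 7.0 / 0.6 = 11.67 months. A median of 5.5 months was also tried.
- Share susceptible: 45% for hyperglycemia, the incidence in the earlier combination study (Protocol 1.2.3.3), used as a scenario only. For rash, 35% is assumed.
- Onset: early patterns follow the two protocol statements; later patterns are assumptions.
- Null condition: onset time O is independent of exposure T.
- Membership: O ≤ T, or O ≤ T + 30 days to reflect SAP 2.1.9. For the medication subset, O is the medication start. Section 3.6.1 gives ATC codes but no time window for that start, so the same window was applied.

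**Simulation, 4,000,000 patients per scenario.** Median exposure from first dose in months, event / non-event patients. The all-patient median is 11.68.

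| Onset scenario | Without window | With 30-day window | Excess of event over all patients, with window |
|---|---|---|---|
| 45%, uniform in month 1 | 12.18 / 11.28 | 11.68 / 11.68 | 0 |
| 35%, uniform in months 0–2 (rash-like) | 12.70 / 11.15 | 11.96 / 11.53 | 0.28 |
| 45%, median 1 month | 13.07 / 10.62 | 12.37 / 11.14 | 0.69 |
| 45%, onset median 0.5 month plus median 1 month to medication | 13.76 / 10.15 | 12.88 / 10.76 | 1.20 |
| 45%, median 2 months | 14.31 / 9.85 | 13.50 / 10.35 | 1.82 |
| Constant hazard, about 45% with event | 21.50 / 6.42 | 20.58 / 6.42 | 8.90 |

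With a true median of 5.5 months, the scenario with onset median 1 month gives 6.83 / 4.59 without the window and 6.14 / 5.02 with it. No scenario made event patients look shorter exposed beyond simulation error.

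**Closed-form check on means.** Let exposure have rate m, onset rate h and window g. Mean exposure in event patients is

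[1/m − e^(−hg)·m/(m+h)²] / [1 − e^(−hg)·m/(m+h)],

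which is 1/m + 1/(m+h) when g = 0. Take an illustrative mean exposure of 7.5 months (m = 0.1333) and g = 30/30.4375 = 0.986 months.
- Early onset, mean 0.7 months (h = 1.4286): without the window, 7.5 + 1/1.5619 = 8.14. With it, e^(−hg) = 0.2446 and the mean is (7.5 − 0.0134) / (1 − 0.0209) = 7.65. The excess falls from 0.64 to 0.15 months.
- Constant hazard of 0.02 per month: without the window, 7.5 + 1/0.1533 = 14.0. With it, 13.2. Here the window barely helps.

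**Landmark alternative under the same null.** Among patients with T beyond the landmark, event status at the landmark depends only on O, which is independent of T. Exposure after the landmark therefore has the same distribution in both groups, and the difference is 0. That equality needs only independence. The common median of 11.67 months also needs the exponential assumption.

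**The case against.** A reader might infer more than the documents support, in two ways.

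The first inference is that a patient must still be on alpelisib/placebo to enter the event group, so exposure will necessarily look longer. SAP 2.1.9 counts events to 30 days after the last dose of any component, and Protocol 6.1.2 and 6.3.1.2 let a patient continue on fulvestrant alone. An event can therefore be counted after alpelisib/placebo has stopped. With hyperglycemia onset confined to month 1, the distortion vanishes. If the event truly shortens exposure, the observed figure may be no longer at all.

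The second inference is that exposure is roughly doubled on placebo, so the contrast between arms is misleading. The arithmetic is right under a constant hazard (14.0 against 7.5 months), but no passage gives an onset pattern for placebo patients, and the SAP specifies no contrast between arms for these tables.

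It is also fair to say that the tables are descriptive and untested, and that other outputs address the clinical question more directly. These are reasons for treatment discontinuation (SAP 3.5), dose reductions, interruptions and permanent discontinuations with reasons (3.6.4), adverse events leading to discontinuation or dose change (3.9.1.4), and time to onset and resolution (3.9.1.5.1, 3.9.2.1).

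These arguments limit the size and consequence of the point. They do not rescue the stated purpose: none of those outputs corrects the five tables or supplies the missing comparator.

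**Conclusion.** The point holds in a limited form. As specified, the five tables cannot assess the impact of hyperglycemia or rash on exposure. If the event does nothing, the grouping tends to lengthen apparent exposure; if the event shortens exposure, it hides part of that effect.

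The distortion is about nil to small for the onset timing the protocol describes once the 30-day window is applied. It is larger for the three medication subsets and for late onset. Whether it differs between arms depends on placebo onset timing, which the documents do not give. The sizes rest on exponential exposure, assumed onset distributions and an assumed share with rash; the direction does not depend on those particular values. The issue is confined to descriptive safety output.

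**What to change.** Keep the five tables, but change the lead-in in SAP 3.6.1 so that it says they describe exposure in patients who developed the event, and drop the claim that they assess impact.

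To assess impact, add a landmark table. Take patients still on alpelisib/placebo at day 29 (hyperglycemia) or day 57 (rash), classify them by event status at that day, and compare exposure after the landmark between those with and without the event, by arm. Beside it, report how many patients stopped alpelisib/placebo before the landmark and why, including stops due to the event itself. The landmark removes those patients, and they carry part of the effect being sought.

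A clock starting at onset is less suitable. Under the SAP's window, onset can follow the last alpelisib/placebo dose, which leaves remaining exposure undefined without a further rule, and it supplies no comparator.

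The cost is a wording change and one or two extra descriptive tables from data already collected. One limitation remains: some patients classed as event-free at the landmark will have the event later, which dilutes the contrast.
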